10.3.5. Reporting of SAEs**SAE Reporting via an Electronic Data Collection Tool**

- The primary mechanism for reporting an SAE will be the electronic data collection tool.

- If the electronic system is unavailable, then the site will use the SAE paper form (see next section) to report the event within 24 hours.
- The site will enter the SAE data into the electronic system as soon as it becomes available.
- After the study is completed at a given site, the electronic data collection tool will be taken offline to prevent the entry of new data or changes to existing data.
- If a site receives a report of a new SAE from a study participant or receives updated data on a previously reported SAE after the electronic data collection tool has been taken offline, then the site can report this information on an SAE paper form (see next section) or to the Sponsor by telephone.
- Contacts for SAE reporting can be found in site training documents.

SAE Reporting via Paper Form

E-mail transmission of the SAE paper form is the preferred method to transmit this information to the Sponsor.

Initial notification via telephone does not replace the need for the investigator to complete and sign the SAE paper form within the designated reporting time frames.

Contacts for SAE reporting can be found in site training documents.

10.3.6. Regulatory Reporting Requirements

SAE Regulatory Reporting

Prompt notification by the investigator to the Sponsor of an SAE is essential so that legal obligations and ethical responsibilities toward the safety of participants and the safety of a study intervention under clinical investigation are met.

The Sponsor has a legal responsibility to notify both the local regulatory authority and other regulatory agencies about the safety of a study intervention under clinical investigation. The Sponsor will comply with country-specific regulatory requirements relating to safety reporting to the regulatory authority, IRB/IEC, and investigators.

An investigator who receives an investigator safety report describing an SAE or other specific safety information (for example, summary or listing of SAEs) from the Sponsor will review and then file it along with the IB and will notify the IRB/IEC, if appropriate according to local requirements.

10.4. Appendix 4: Contraceptive and Barrier Guidance

10.4.1. Definitions

Females of childbearing potential

Adult females are considered WOCBP unless they are WNOCBP.

Females not of childbearing potential

Females are not considered WOCBP if they

- do not have a uterus, including having a congenital condition such as Mullerian agenesis
- are infertile due to surgical sterilization, or
- are postmenopausal.

Examples of surgical sterilization include

- total hysterectomy
- bilateral salpingo-oophorectomy
- bilateral salpingectomy, or
- bilateral oophorectomy.

Postmenopausal state

The postmenopausal state should be defined as a woman

- at any age, at least 6 weeks post-surgical bilateral oophorectomy with or without hysterectomy, confirmed by operative note
- at least 40 years of age and up to 55 years old with an intact uterus, not on hormone therapy^a, who has had cessation of menses for at least 12 consecutive months without an alternative medical cause, AND with follicle-stimulating hormone levels >40 mIU/mL
- 55 years of age or older not on hormone therapy, who has had at least 12 months of spontaneous amenorrhea, or
- at least 55 years of age with a diagnosis of menopause prior to starting hormone replacement therapy.

^aWomen should not be taking medications during amenorrhea such as oral contraceptives, hormones, gonadotropin-releasing hormone, anti-estrogens, selective estrogen receptor modulators, or chemotherapy that could induce transient amenorrhea.

10.4.2. Contraception Guidance

Guidance for women of childbearing potential

WOCBP who are completely abstinent as their preferred and usual lifestyle, or in a same-sex relationship as their preferred and usual lifestyle:

Must...	Must not...
agree to either remain abstinent or stay in a same-sex relationship without sexual relationships with males	
 use periodic abstinence methods 
 calendar ovulation symptothermal, or post-ovulation declare abstinence just for the duration of a trial, or use the withdrawal method

WOCBP who are NOT completely abstinent as their preferred and usual lifestyle, or NOT in a same-sex relationship as their preferred and usual lifestyle, must do the following:

Topic	Condition
Pregnancy testing	Have a negative serum test result at screening followed by a negative urine and serum result at enrollment. See the protocol Schedule of Activities for subsequent pregnancy testing requirements.
Contraception	
Agree to use 1 highly effective method (less than 1% failure rate) of contraception or a combination of 2 effective methods of contraception
 
These forms of contraception must be used for the duration of the study.

Guidance for all men

No male contraception is required except in compliance with specific local government study requirements.

Examples of different forms of contraception

Methods	Examples
Highly effective contraception (<1% failure rate)	
 female sterilization combination oral contraceptive pill progestin-only contraceptive pill (mini-pill) implanted contraceptives injectable contraceptives contraceptive patch (only women weighing <198 pounds or <90 kg) total abstinence vasectomy (if only sexual partner) fallopian tube implants (if confirmed by hysterosalpingogram) combined contraceptive vaginal ring, or intrauterine devices

Effective contraception	
• barrier method with use of a spermicide
○ male condom with spermicide○ diaphragm with spermicide or cervical sponge, or○ female condom with spermicide 
Note: The barrier method must include use of a spermicide (i.e., condom with spermicide, diaphragm with spermicide, or female condom with spermicide) to be considered effective.

Ineffective forms of contraception whether used alone or in any combination	
• spermicide alone• periodic abstinence• fertility awareness (calendar method, temperature method, cervical mucus, or symptothermal)• withdrawal• postcoital douche, or• lactational amenorrhea

10.5. Appendix 5: Liver Safety: Suggested Actions and Follow-Up Assessments

Hepatic evaluation testing

The Lilly-designated central laboratory must complete the analysis of all selected testing except for microbiology testing.

Local testing may be performed *in addition to central testing* when necessary for immediate participant management.

Results will be reported if a validated test or calculation is available.

Hematology		Clinical Chemistry
Hemoglobin		Total bilirubin
Hematocrit		Direct bilirubin
Erythrocytes (RBCs - red blood cells)		Alkaline phosphatase
Leukocytes (WBCs - white blood cells)		Alanine aminotransferase
Differential:		Aspartate aminotransferase
Neutrophils, segmented		Gamma-glutamyl transferase
Lymphocytes		Creatine kinase
Monocytes		Other Chemistry
Basophils		Acetaminophen
Eosinophils		Acetaminophen protein adducts
Platelets		Alkaline phosphatase isoenzymes
Cell morphology (RBC and WBC)		Ceruloplasmin
Coagulation		Copper
Prothrombin time, INR		Ethyl alcohol
Serology		Haptoglobin
Hepatitis A virus testing:		Immunoglobulin A (quantitative)
HAV total antibody		Immunoglobulin G (quantitative)
HAV IgM antibody		Immunoglobulin M (quantitative)
Hepatitis B virus testing:		Phosphatidylethanol (PEth)
Hepatitis B surface antigen		Urine Chemistry
Hepatitis B surface antibody		Drug screen
Hepatitis B core total antibody		Ethyl glucuronide
Hepatitis B core IgM antibody		Other Serology
Hepatitis B core IgG antibody		Anti-nuclear antibody
HBV DNA ^b		Anti-smooth muscle antibody ^a
		Anti-actin antibody ^c

Hematology	Clinical Chemistry
Hepatitis C virus testing:	Epstein-Barr virus testing:
HCV antibody	EBV antibody
HCV RNA ^b	EBV DNA ^b
Hepatitis D virus testing:	Cytomegalovirus testing:
HDV antibody	CMV antibody
Hepatitis E virus testing:	CMV DNA ^b
HEV IgG antibody	Herpes simplex virus testing:
HEV IgM antibody	HSV (Type 1 and 2) antibody
HEV RNA ^b	HSV (Type 1 and 2) DNA ^b
Microbiology^d	Liver kidney microsomal type 1 antibody
Culture:	
Blood	
Urine	

a Not required if anti-actin antibody is tested.

b Reflex/confirmation dependent on regulatory requirements, testing availability, or both.

c Not required if anti-smooth muscle antibody (ASMA) is tested.

d Assayed ONLY by investigator-designated local laboratory; no central testing available.

10.6. Appendix 6: Provisions for Changes in Study Conduct During Exceptional Circumstances

Implementation of this appendix

The changes to procedures described in this appendix are temporary measures intended to be used only during specific time periods as directed by the Sponsor in partnership with the investigator.

Exceptional circumstances

Exceptional circumstances are rare events that may cause disruptions to the conduct of the study. Examples include pandemics or natural disasters. These disruptions may limit the ability of the investigators, participants, or both to attend onsite visits or to conduct planned study procedures.

Implementing changes under exceptional circumstances

In an exceptional circumstance, after receiving the Sponsor's written approval, sites may implement changes if permitted by local regulations.

After approval by local ERBs, regulatory bodies, and any other relevant local authorities, implementation of these exceptional circumstance changes will not typically require additional notification to these groups, unless they have specific requirements in which notification is required, for example, upon implementation and suspension of changes. All approvals and notifications must be retained in the study records.

If the Sponsor grants written approval for changes in study conduct, the Sponsor will also provide additional written guidance, if needed.

Considerations for making a change

The prevailing consideration for making a change is ensuring the safety of study participants. Additional important considerations for making a change are compliance with GCP, enabling participants to continue safely in the study and maintaining the integrity of the study.

Informed consent

Additional consent from the participant will be obtained, if required, for

- participation in remote visits, as defined in Section “Remote Visits”
- dispensation of additional study intervention during an extended treatment period
- alternate delivery of study intervention and ancillary supplies, and
- provision of their personal or medical information required prior to implementation of these activities.

Changes in study conduct during exceptional circumstances

Changes in study conduct not described in this appendix, or not consistent with applicable local regulations, are not allowed.

The following changes in study conduct will not be considered protocol deviations:

Remote visits***Types of remote visits***

Telemedicine: Telephone- and/or technology-assisted virtual visits are acceptable to complete appropriate assessments according to the SoA, if written approval is provided by the Sponsor.

Mobile healthcare: Healthcare visits may be performed by a mobile healthcare provider at locations other than the study site when participants cannot travel to the site due to an exceptional circumstance if written approval is provided by the Sponsor.

Other alternative locations: Laboratory draws may be done at an alternate location in exceptional circumstances, if written approval is provided by the Sponsor.

Data capture

In source documents and the CRF, the study site should capture the visit method, with a specific explanation for any data missing because of missed in-person site visits.

Safety reporting

Regardless of the type of remote visits implemented, the protocol requirements regarding the reporting of AEs, SAEs, and PCs remain unchanged.

Return to onsite visits

Every effort should be made to enable participants to return to onsite visits as soon as reasonably possible, while ensuring the safety of both participants and site staff.

Local laboratory testing option

Local laboratory testing may be conducted in lieu of central laboratory testing, except for HbA1c and serum glucose testing. Lilly-designated laboratory testing must be retained for HbA1c and serum glucose.

The local laboratory must be qualified in accordance with applicable local regulations.

Obtain local labs for safety hematology, chemistry, hormone panel, and urinalysis, when applicable, per the SoA. Safety labs should be obtained as specified in the SoA.

All labs will be reviewed by the investigators. Sign and date review of local labs per normal process and follow-up with the participant as needed. Results will not be recorded in the CRF.

Lilly Medical should be informed of any labs that meet criteria for temporary or permanent study intervention discontinuation.

Study intervention and ancillary supplies (including participant diaries)

When a participant is unable to go to the site to receive study supplies during normal onsite visits, the site should work with the Sponsor to determine appropriate actions. These actions may include

- asking the participant to go to the site and receive study supplies from site staff without completion of a full study visit
- asking the participant's designee to go to the site and receive study supplies on a participant's behalf, and

- arranging delivery of study supplies.

These requirements must be met before action is taken.

- Alternate delivery of study intervention should be performed in a manner that does not compromise treatment blinding and ensures product integrity. The existing protocol requirements for product accountability remain unchanged, including verification of participant's receipt of study supplies.
- When delivering supplies to a location other than the study site, for example, participant's home, the investigator and/or the Sponsor should ensure oversight of the shipping process to ensure accountability and product quality, that is, storage conditions maintained and intact packaging upon receipt.
- Instructions may be provided to the participant or designee on the final disposition of any unused or completed study supplies.

Screening period guidance

To ensure safety of study participants, laboratory values and other eligibility assessments taken at screening or the lead-in visits are considered valid for a maximum of 24 days. The following rules will be applied for active, non-enrolled participants whose participation in the study must be paused due to exceptional circumstances:

- If screening is paused for less than 24 days from the signing of the ICF to the start of treatment, the participant will proceed to the next study visit per the usual SoA, provided that the treatment is started within 30 days from first screening.
 - The site should conduct the next visit if the participant's eligibility criteria are confirmed, and the site should document the reason for delay.
 - Due to the pause in screening, sites should also reconfirm the impacted participant's consent and document this confirmation in the source documentation.
- If screening is paused for more than 24 days from signing of the ICF to the start of treatment, the participant must be discontinued because of screening interruption due to an exceptional circumstance. This is documented as a screen failure in the CRF. The participant can reconsent and be rescreened as a new participant. The screening procedures per the usual SoA should be followed, starting at the screening visit to ensure participant eligibility by the randomization visit.

Adjustments to visit windows

Whenever possible and safe to do so, as determined by the investigator's discretion, participants should complete the usual SoA. To maximize the possibility that these visits can be conducted as onsite visits, the windows for visits may be adjusted, upon further guidance from the Sponsor. This minimizes missing data and preserves the intended conduct of the study.

For participants whose visits have extended windows, additional study intervention may need to be provided to avoid interruption and maintain overall integrity of the study.

Documentation***Changes to study conduct will be documented***

Sites will identify and document the details of how participants, visit types, and conducted activities were affected by exceptional circumstances. Dispensing or shipment records of study intervention and relevant communications, including delegation, should be filed with site study records.

Source documents at alternate locations

Source documents generated at a location other than the study site should be part of the investigator's source documentation and should be transferred to the site in a secure and timely manner.

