- In addition, the Sponsor or its representatives will periodically check a sample of the participant data recorded against source documents at the study site. The study may be audited by the Sponsor or its representatives and/or regulatory agencies at any time. Investigators will be given notice before an audit occurs.

Data capture system

An EDC will be used in this study for the collection of data. The site will maintain a separate source for the data entered by the site into the Sponsor-provided EDC system. The investigator is responsible for the identification of any data to be considered as source data and for confirming that data reported are accurate and complete by signing the CRF.

Any data, for which paper documentation provided by the subject will serve as the source document, will be identified and documented by each site in that site's study file. Paper

documentation provided by the subject may include subject diary. Data from these paper documentations will be transcribed to eCRFs at the sites.

eCRF data will be encoded and stored in a clinical trial database. Data managed by a central vendor will be stored electronically in the central vendor's database system. The investigator will have continuous access to the data during the study and until decommissioning of the data capture system. Prior to decommissioning, the investigator will receive or access an archival copy of pertinent data for retention.

Data managed by a central vendor, such as laboratory test data, will be stored electronically in the central vendor's database system, and reports will be provided to the investigator for review and retention. Data will subsequently be transferred from the central vendor to the Sponsor data warehouse.

Data from complaint forms submitted to the Sponsor will be encoded and stored in the global product complaint management system.

The investigator is responsible for ensuring the accuracy, completeness, legibility, and timeliness of the data reported to the Sponsor.

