10.2. Appendix 2: Clinical Laboratory Tests

The tests detailed in the table here will be performed by the Lilly-designated laboratory or by the local laboratory, as specified in the table.

Local laboratory results are only required if the central laboratory results are not available in time for study intervention administration and/or response evaluation. If a local sample is required, it is important that the sample for central analysis is obtained at the same time.

Additionally, if the local laboratory results are used to make either a study intervention decision or response evaluation, the results must be recorded.

In circumstances where the Sponsor approves local laboratory testing in lieu of central laboratory testing (in the table), the local laboratory must be qualified in accordance with applicable local regulations.

Protocol-specific requirements for inclusion or exclusion of participants are detailed in Section 5 of the protocol.

Additional tests may be performed at any time during the study as determined necessary by the investigator or required by local regulations.

Investigators must document their review of the laboratory safety results.

Clinical Laboratory Tests	Comments
Hematology	Assayed by Lilly-designated laboratory
Hemoglobin	
Hematocrit	
Erythrocyte count (red blood cells)	
Mean cell volume	
Mean cell hemoglobin	
Mean cell hemoglobin concentration	
Leukocytes (WBCs - white blood cells)	
Differential	
Percent and absolute count of	
Neutrophils, segmented	
Lymphocytes	
Monocytes	
Eosinophils	
Basophils	
Platelets	
Clinical Chemistry	Assayed by Lilly-designated laboratory
Sodium	
Potassium	
Total bilirubin	
Direct bilirubin	
Alkaline phosphatase	
Alanine aminotransferase	
Aspartate aminotransferase	

Clinical Laboratory Tests	Comments
Gamma-glutamyl transferase	
Blood urea nitrogen	
Creatinine	
Uric acid	
Total protein	
Albumin	
Glucose	Fasting at baseline and Week 24
Cholesterol	
Triglycerides	
Lipid Panel	Assayed by Lilly-designated laboratory
High-density lipoprotein	
Low-density lipoprotein (LDL-C)	This value will be calculated. If triglycerides >400 mg/dL, the direct LDL will be assayed
Very-low-density lipoprotein (VLDL-C)	
Urinalysis	Assayed by Lilly-designated laboratory
Specific gravity	
pH	
Protein	
Glucose	
Ketones	
Bilirubin	
Urobilinogen	
Blood	
Nitrite	
Urine leukocyte esterase	
Microscopic examination of sediment	
Hormones (female)	
Serum pregnancy	Assayed by Lilly-designated laboratory

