16.2 Analysis

Population: SAF and PP

Stratification: Table: Add the strata as needed in case subjects with dose modification exceeding 20% based on enrolled population as per section 7.3:

- a. Subjects on 1.5 mg only
- b. Subjects on 0.75 mg only
- c. Subjects with any dose modification*

* Subjects who have received at least one dose of 1.5 mg and at least one dose of 0.75 mg

Listing: by subject, visit and each laboratory test parameter

Statistics: Summaries of all the laboratory tests will include descriptive statistics of the following:

- Actual and change from baseline (number of patients, mean, SD, median, minimum, maximum, and interquartile ranges) (for quantitative measurements)
- Frequencies and percentages (n and %) (for qualitative measurements)

All the laboratory tests will be listed separately and listing of abnormal laboratory test will be presented.

Continuous chemistry and hematology measures will be summarized as change from baseline to Week 24 using the general linear model, with the baseline value of the response variable as covariate and the estimate and 95% CI will be presented. In addition, a descriptive analysis for actual value and change from baseline will be performed

using LOCF. It will be performed using the baseline or 12-week value, if the 24-week value is missing.

17. Vital signs

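### If the Appendix 6 local laboratory option is used, measured safety values have no described route into the analysis database, and the SAP does not say how to handle the gap

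*Protocol*

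**What the plan says.** Protocol 10.6 (Appendix 6) provides that "Local laboratory testing may be conducted in lieu of central laboratory testing, except for HbA1c and serum glucose testing". It directs sites as follows: "Obtain local labs for safety hematology, chemistry, hormone panel, and urinalysis, when applicable, per the SoA". Investigators review and sign the reports, and the sponsor's medical team is told of results that meet discontinuation criteria. On data capture the text is unqualified: "Results will not be recorded in the CRF".

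The option is restricted. "The changes to procedures described in this appendix are temporary measures intended to be used only during specific time periods", and only after the Sponsor's "written approval, sites may implement changes if permitted by local regulations".

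Four other places bear on it:

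- **Protocol 10.2 (Appendix 2):** "if the local laboratory results are used to make either a study intervention decision or response evaluation, the results must be recorded". The same appendix asks for a simultaneous central sample when a local one is needed, but also foresees sponsor-approved local testing in place of central testing.
- **Protocol 10.5 (Appendix 5):** hepatic evaluation tests other than microbiology must be analysed centrally, and local testing comes on top of that.
- **Protocol 10.1.6:** participant data go on CRFs unless sent electronically. "Data managed by a central vendor, such as laboratory test data, will be stored electronically" in that vendor's system and then passed to the sponsor.
- **SAP 16.2:** laboratory tests are summarised as observed values and changes, fitted with a general linear model for change to Week 24, and listed, with a separate listing of abnormal results. A further descriptive LOCF analysis is added: "It will be performed using the baseline or 12-week value, if the 24-week value is missing".

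**The concern.** The primary objective is safety, and hematology and chemistry are drawn only twice on treatment, at Visit 5 (Week 12) and Visit 8 (Week 24). A result obtained locally under Appendix 6 is a real on-treatment measurement, reviewed by the investigator, yet no text brings it to the statistician. In the dataset, a test that was done but not captured would look the same as a test that was never done. The SAP would then treat the value as missing and, in one table, substitute an older one.

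The instruction also meets Appendix 2 at an awkward place. Appendix 6 expects that some local results will bear on stopping treatment, and those are the results that Appendix 2 wants recorded. Appendix 6 exempts only HbA1c and serum glucose from local substitution, so on its face it also covers the hepatic tests that Appendix 5 keeps central. Sites hold all three instructions, so the tension exists even if the option is never activated.

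**Working it through.** **1. The plan's own figures.** Protocol 9.6 gives 250 screened, 20% screen failure and 20% dropout. 250 × (1 − 0.20) = 200 treated; 200 × (1 − 0.20) = 160 completers. Both reproduce.

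**2. Routes into the database.** Protocol 10.1.6 gives two: the CRF, and electronic transmission. Appendix 6 closes the first for local safety results. The second is described for laboratory data only from the central vendor. No third route is described.

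**3. What each SAP 16.2 output does with a local-only Week 24 visit.**

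- By-visit summaries and abnormal-value listing: the value is absent.
- General linear model: no imputation is named for it, and SAP 7.5 calculates change only when both values exist. The patient apparently drops out.
- Supplementary LOCF table: Week 12 is carried if it was captured. If Visit 5 was also local-only, baseline is carried and the change is exactly 0.
- Lipid panel, eGFR and urinary albumin/creatinine ratio have no scheduled Week 12 value (Protocol 1.3). If the LOCF table covers them, only baseline can be carried and the change is 0.

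**4. Share of a patient's data.** One local-only visit of two removes 1/2 = 50% of the on-treatment hematology and chemistry panels; two remove 100%.

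**5. Size across an assumed range.** Let f be the share of the 160 completers whose Week 24 panel is local-only. The documents give no value, so f is assumed.

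- Missing panels = 160 × f; observed n = 160 × (1 − f).
- LOCF mean change ÷ true mean change = 1 − f(1 − r), where r is the part of the Week 24 change already present in the carried value. For baseline r = 0; for Week 12, r = 0.5 and 0.8 are assumed. Affected patients are assumed to have the same true mean change as the rest.
- One-sided 95% upper bound when no abnormality is seen = 1 − 0.05^(1/n).
- Chance of seeing at least one abnormality of 1% frequency = 1 − 0.99^n.

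| f | Missing | n | LOCF ratio, baseline | LOCF ratio, Week 12 (r = 0.5 / 0.8) | Zero-event bound | Chance of ≥1 |
|---|---|---|---|---|---|---|
| 0 | 0 | 160 | 1.00 | 1.00 / 1.00 | 1.85% | 80.0% |
| 5% | 8 | 152 | 0.95 | 0.975 / 0.99 | 1.95% | 78.3% |
| 10% | 16 | 144 | 0.90 | 0.95 / 0.98 | 2.06% | 76.5% |
| 20% | 32 | 128 | 0.80 | 0.90 / 0.96 | 2.31% | 72.4% |
| 40% | 64 | 96 | 0.60 | 0.80 / 0.92 | 3.07% | 61.9% |

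The last two columns concern abnormalities visible in the Week 24 laboratory data, not those reported as AEs.

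**The case against.** The strongest defence is that patients stay protected and the primary endpoints stay intact. Protocol 8.2.4 requires clinically relevant laboratory changes to be reported as AEs and results to be kept with source documents. Appendix 6 leaves AE reporting unchanged for remote visits. The primary endpoints are AEs, and continuous laboratory measures fall under other safety analyses (Protocol 9.4.5). This stands, and it limits the point to laboratory data. It does not close the gap: an AE record does not supply the value for the laboratory tables, and shifts that the investigator does not judge clinically relevant leave no trace.

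Second, Appendix 2 asks for results to be recorded without naming the CRF, so an entry in source documents meets it literally. It also accepts local testing in place of central testing with sponsor approval. This softens a contradiction into a tension, but two appendices that a site could read in opposite ways still need reconciling.

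Third, the missing route is inferred from silence. Electronically sent data are exempt from the CRF, and Appendix 6 promises further written guidance if needed. A local transfer could therefore be arranged, but nothing in either document plans one.

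Fourth, HbA1c and serum glucose must stay central, and HbA1c is drawn at Visits 5 and 8. Where a central HbA1c sample can be taken, central chemistry often could be too, so two local-only visits in one patient are less likely. That is fair, and it argues for the low end of the range.

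Finally, keeping local values out of pooled means is defensible, because subtracting a central baseline from a local value adds between-laboratory error. This stands and shapes the fix.

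**Conclusion.** The point holds as a conditional gap in data capture and analysis. For visits that use the Appendix 6 option, measured safety values have no described path to the SAP 16.2 outputs, and the SAP says nothing about them. The effect is nil if the option is never used. With an assumed 5% to 40% of 160 completers affected, 8 to 64 Week 24 panels are missing, and the supplementary LOCF mean change falls to between 99% and 60% of its true value, depending on which value is carried. These figures rest on the assumed f and r and on affected patients resembling the others.

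A reader might infer more, and four stronger readings are not supported:

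- **That on-treatment safety laboratory data are lost in general.** The option is temporary and needs sponsor approval, and central testing is otherwise the rule.
- **That older values replace Week 24 values in the main laboratory analysis.** LOCF is an additional descriptive table; the other outputs lose the patient instead of filling the value.
- **That the loss is one-sided and hides abnormal results.** Appendix 6 omits normal and abnormal results alike, and AE reporting favours capture of the abnormal ones. What can be said is that LOCF pulls towards earlier values.
- **That baseline liver values would be missing if Visit 2 were local.** Chemistry is also drawn at screening, and SAP 7.2 takes the last non-missing value before the first dose.

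The primary endpoints are not threatened. The point deserves action because the trial is about safety and the repair is cheap.

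**What to change.** **Protocol.** Replace the Appendix 6 sentence so that local results obtained in place of central testing are entered in the CRF or an external data transfer, with value, units, reference range, date and nominal visit, and flagged as local. The nominal visit matters because SAP 7.1 leaves unscheduled measurements out of by-visit summaries. Reconcile Appendices 2, 5 and 6 on which local results are recorded, where, and whether local substitution extends to hepatic evaluation tests.

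**SAP 16.2.** State that:

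- flagged local values appear in the laboratory and abnormal-value listings, classified against the local reference range;
- the number of visits with local-only results is reported;
- LOCF is not applied where a local result exists;
- the continuous summaries and the general linear model stay central-only, and any analysis that adds local values is a sensitivity analysis.

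**Cost.** A few sentences in each document, a contingency CRF page or transfer specification used only if the option is activated, and some data entry. Local units and ranges bring heterogeneity, which the flag and the central-only main summaries contain.
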